#### 4.5.2.2. Impact of COVID-19 Pandemic on Safety Results

Since all subjects are dosed after the pandemic started, the outputs showing the incidence rates for events occurring before or after the start of the COVID-19 pandemic are not applicable.

### 4.5.3. Additional Safety Assessments

Any additional safety data will be produced using listings via RAPIDO data viewer. This includes a listing of liver monitoring/stopping event reporting, liver stopping event profile, ECOG performance status, and LVEF.

#### 4.5.4. Deaths

All deaths will be summarized based on the number and percentage of participants. This summary will classify participants by time of death relative to the last dose of medication (>30 days or  $\leq$ 30 days) and primary cause of death in the order listed in the eCRF. A supportive listing will be generated to provide participant-specific details on participants who died.

### 4.5.5. Pregnancies

While pregnancy itself is not considered to be an AE or SAE, any pregnancy complication or elective termination of a pregnancy for medical reasons will be reported as an AE or SAE.

# 4.6. Other Analyses

Data from all participating centres will be integrated and no controlling for center-effect will be considered in the statistical analyses.

### 4.7. Interim Analyses

Due to study termination, no interim analyses will be conducted.

# 4.8. Changes to Protocol Defined Analyses

Study termination occurred just as Part 1 (dose escalation) had finished recruitment. Therefore, no participants will be recruited to Part 2 of study design mentioned within the protocol (Dated: 25-Jan-2022) and hence no data will be collected or analysed. Additionally, no interim analyses will occur as there is no need to initiate Part 2.

### 5. SAMPLE SIZE DETERMINATION

Approximately 72 participants were planned to be enrolled to receive study intervention. The planned sample size for the study was chosen to allow adequate characterization of safety, clinical activity, PK, and PD profile based on the study objectives. For Part 1 dose escalation, the total sample size will depend on the number needed to adequately characterize the DLT profile and determine the MTD. For Part 2 dose expansion, approximately 50 participants were planned to be recruited. Refer to Section 9.2 of the protocol for details regarding sample size determination, statistical design, and operating characteristics.

### 6. SUPPORTING DOCUMENTATION

# 6.1. Appendix 1 Study Population Analyses

Unless otherwise specified, the study population analyses will be based on the Safety Analysis Set.

In this multicentre global study, enrolment will be presented by country and site.

### 6.1.1. Participant Disposition

A summary of the number and percentage of participants who completed the study as well as those who prematurely withdrew from the study or died will be provided. Reasons for study withdrawal will be listed. For those who have neither completed, died, nor withdrawn, they will be categorized as on study intervention or in follow up.

A participant is considered to have completed the study if they have completed all phases of the study including the last visit or the last scheduled procedure shown in the Schedule of Activities (Section 1.3 of the protocol). In addition, if the sponsor decides to close the study, participants who are receiving study intervention or are in the follow-up period will be considered to have completed the study.

A summary of study intervention status will be provided. This display will show the number and percentage of participants who have completed the scheduled study intervention, are ongoing with study intervention, died, or have discontinued study intervention prematurely, as well as primary reasons for discontinuation of study intervention. Reasons for study treatment discontinuation will be listed.

A listing of reasons for screen failure will be provided using the screened population. A listing of subjects excluded from any population, and a listing of subjects with inclusion/exclusion criteria deviations will be reported.

# 6.1.2. Demographic and Baseline Characteristics

The demographic characteristics including age, gender, ethnicity, height/weight at screening and race will be summarized with descriptive statistics using the Safety population. In addition, the following age categories will be summarized: 18-64, 65-84 and >=85 based on the Enrolled Analysis Set.

Disease characteristics at screening including primary tumor type, time since initial diagnosis, disease classification (WHO classification of AML or MDS and IPSS-R category), blast count percentage, and cytogenetics and molecular alterations will be summarized and listed. The following genetic markers have been identified by the study team for inclusion in displays: IDH1, IDH2, NPM1, FTL3, NRAS, c-KIT, TP53, CEBPA.

#### 6.1.3. Protocol Deviations

Important protocol deviations will be listed.

Protocol deviations will be tracked by the study team throughout the conduct of the study. These protocol deviations will be reviewed to identify those considered as important as follows:

- Data will be reviewed prior to freezing the database to ensure all important deviations (where possible without knowing the study intervention details) are captured and categorised in the protocol deviations dataset.
- This dataset will be the basis for the summaries of important protocol deviations.

#### 6.1.4. Prior and Concomitant Medications

Concomitant medications will be coded using the WHO Drug dictionaries. A listing of concomitant medications using ingredient will be produced.

Concomitant medications include any medication that was taken at some point during the on-intervention period as defined in Section 6.2.1.1.

### 6.1.5. Prior Anti-cancer Therapy

The number and percentage of participants that received any prior anti-cancer therapy or stem cell transplant will be summarized. Prior anti-cancer therapy will be summarized by ingredient.

### 6.1.6. Additional Analyses Due to the COVID-19 Pandemic

The incidence of AEs and SAEs (fatal and non-fatal) of COVID-19, COVID-19 AEs leading to study drug discontinuation or study withdrawal, and COVID-19 AEs by severity, will be obtained from standard AE and SAE summaries.

Since all subjects are dosed after the pandemic started and the outputs showing the incidence rates for events occurring before or after the start of the COVID-19 pandemic are not applicable.

## 6.2. Appendix 2 Data Derivations Rule

### 6.2.1. Criteria for Potential Clinical Importance

Reference ranges for all laboratory parameters collected throughout the study are provided by the laboratory. A laboratory value that is outside the reference range is considered either high abnormal (value above the upper limit of the reference range) or low abnormal (value below the lower limit of the reference range). Note: a high abnormal or low abnormal laboratory value is not necessarily of clinical concern.

National Cancer Institute Common Terminology Criteria for Adverse Events (NCI-CTCAE v4.0.3) will be used to assign grades to the relevant laboratory parameters, including clinical chemistry, hematology, coagulation, liver function tests, QTc (Fridericia's) values, and vital signs (heart rate, blood pressure, temperature, respiratory rate).

#### 6.2.1.1. ECG

ECG Parameter	Units	Clinical Concern Range		cern Range
			Lower	Upper
	Absolu	te		
		Grade 1	≥ 450	< 481
Absolute QTcF Interval	msec	Grade 2	≥ 481	< 501
		Grade 3	≥ 501	
	Change from Baseline			
Increase from Baseline	msec		> 30	≤ 60
QTcF	msec		> 60	

### **6.2.1.2.** Vital Signs

Vital Sign Parameter	Units		Clinical Concern Range	
(Absolute)			Lower	Upper
Systolic Blood Pressure	mmHg	Grade 1	≥120	<140
	mmHg	Grade 2	≥140	<160
	mmHg	Grade 3	≥160	
Diastolic Blood Pressure	mmHg	Grade 1	≥ 80	< 90
	mmHg	Grade 2	≥ 90	< 100
	mmHg	Grade 3	≥ 100	
Heart Rate	bpm	L/H	< 60	> 100
Temperature	Degrees C	L/H	≤ 35	≥ 38
Respiratory Rate	Breaths/min	L/H	<12	≥ 25

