### Table 5Risk Assessment

Potential Risk of	Summary of Data/Rationale for Risk	Mitigation Strategy
Clinical		
Significance		
Investigational Pro		
Cytokine release syndrome (CRS)	
 
Nonclinical: The severity of cytokine related symptoms/signs observed in an AML population is not expected to be more severe than that observed to date in the solid tumor population of Study 2008850 and based on the non-clinical data.
 
Clinical: In Study 208850, dose dependent cytokine-related symptoms and CRS were observed. Symptoms reported with CRS commonly comprised pyrexia, chills/rigors, tachycardia, hypotension, hypoxia, and headache; these were all Grade 1 or 2 events, with none of the cases being life threatening or fatal.
 
Preliminary analyses suggest that cytokine-related AEs may be more likely associated with drug exposure (AUC-related) than measured cytokine levels.
 
	
 
General Measures: 
 
Sites selected based on cytokine release syndrome (CRS) management capabilities (i.e. ICU proximity, staff experience, resuscitation measures, central line placement and medication administration capability).
 
CRS events are categorized as Adverse Events of Special interest (AESIs) which must be reported to the Medical Monitor within 24 hours regardless of study drug relationship.
 
 
 
Monitoring: 
 
Careful observation with continuous in-hospital monitoring throughout the 2-week induction daily-dosing period of the cycle, and 24hr hospital observation post-dose for maintenance dosing.
 
 
 
Mitigation: 
 
Use a starting dose of 12.5 µg that is 1/32nd of the 400 µg MTD (refer to Section 4.4.2).
 
Dose staggering of participants to allow assessment initial safety data before enrolling next participant.
 
 
 

		provided in Table 11 and dose modifications in Section 6.4.1.
Tumor Lysis	In vitro, GSK3745417 shows direct cell killing of AML cells. AML	General measures:
syndrome	population typically has a high risk for TLS with additional risk factors	• Admission to hospital 24hrs prior to each dose for prophylaxis against TLS (Refer to Section 4.1.1).

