## 9.4.2.4. Other Safety Analyses

Data for vital signs and ECGs will be summarized based on predetermined criteria identified to be of potential clinical concern. Further details will be provided in the SAP.

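### SAP 6.2.1.2 sets clinical-concern limits for blood pressure in the upward direction only, so a summary built on them cannot show low blood pressure

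*SAP*

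**What the plan says.** Protocol 9.4.2.4 makes the commitment: "Data for vital signs and ECGs will be summarized based on predetermined criteria identified to be of potential clinical concern". It leaves the details to the SAP. SAP 6.2.1 includes "vital signs (heart rate, blood pressure, temperature, respiratory rate") among the measurements to be graded, and SAP 6.2.1.2 prints the limits.

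- The entry for "Systolic Blood Pressure" starts at "Systolic Blood Pressure mmHg Grade 1 ≥120 <140" and rises through two further bands, from 140 and from 160 mmHg.
- Diastolic pressure starts at "Diastolic Blood Pressure mmHg Grade 1 ≥ 80 < 90" and rises through two further bands, from 90 and from 100 mmHg.
- The other three parameters are two-sided, for example "Heart Rate bpm L/H < 60 > 100" and "Temperature Degrees C L/H ≤ 35 ≥ 38". Respiratory rate is low below 12 and high from 25 breaths per minute.

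The SAP prints no other numerical blood-pressure criterion. SAP 6.2.5 adds a counting rule: a participant with both high and low post-baseline values is counted in both categories, and the rule extends to the relevant tables of potential clinical importance.

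On the clinical side, Protocol Table 5 reports from the solid-tumour study of the same drug: "Symptoms reported with CRS commonly comprised pyrexia, chills/rigors, tachycardia, hypotension, hypoxia, and headache". Protocol Table 11 uses hypotension, alongside hypoxia, to define CRS Grades 2, 3 and 4.

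**The concern.** The pressure change the protocol anticipates from this drug's main acute toxicity is a fall, but the SAP's limits register only high values. A table built on them would show no participant with low blood pressure at any dose level, whatever was recorded. It would also fill with readings from 120/80 mmHg upward.

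A reader of the study report could take the empty low side as evidence that pressure did not fall, when the criteria could not have detected a fall. The data exist to do better: the Schedule of Activities (Protocol Table 1) plans nine vital-sign readings around the dose on each of Days 1, 5, 8 and 12, from pre-dose to 24 hours after the end of injection.

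**Working it through.** The plan states no figure to reproduce. The check applies the printed limits to possible readings and then asks whether the limits still feed an output.

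**Step 1: apply the limits in SAP 6.2.1.2.** The rule for systolic pressure is Grade 3 if ≥160, Grade 2 if ≥140, Grade 1 if ≥120, otherwise no flag. For diastolic pressure it is Grade 3 if ≥100, Grade 2 if ≥90, Grade 1 if ≥80, otherwise no flag.

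| Parameter | Low-side values tried | Low-side result | First high flag |
|---|---|---|---|
| Systolic (mmHg) | every integer 0 to 119 | 0 of 120 flagged | 120 |
| Diastolic (mmHg) | every integer 0 to 79 | 0 of 80 flagged | 80 |
| Heart rate (bpm) | 50 | low flag | above 100 |
| Temperature (°C) | 34.9 | low flag | 38 |
| Respiratory rate (breaths/min) | 10 | low flag | 25 |

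Only blood pressure lacks a low side. The table is otherwise complete, with three bands printed for each pressure, so this does not look like a redaction or an extraction gap.

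**Step 2: ask whether the limits are still in use.** The evidence points both ways.

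- For: Protocol 9.4.2.4 promises the summary. SAP section 1 keeps the planned Part 1 analyses. SAP 4.8, which records departures from the protocol, lists only the loss of Part 2 and of the interim analyses. SAP 6.2.5 still refers to tables of potential clinical importance.
- Against: SAP 4.5 describes no vital-sign table. SAP 4.5.3 sends additional safety data to listings, and the examples it names do not include vital signs. Display specifications sit in a separate output document that is not among those reviewed.

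On the text available, the summary has not been withdrawn, but neither has it been specified.

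**Step 3: find where else low pressure would appear.** An abnormal vital sign that the investigator judges clinically significant is an adverse event (Protocol 10.3.1). Adverse events are summarized and listed (SAP 4.2.2). Haemodynamic toxicity needing vasopressors or other significant intervention falls under the cytokine-related events of special interest, and CRS events have their own summary (SAP 4.3.2). Each of these routes depends on an investigator reporting an event; none applies a pre-specified limit to the measured pressure.

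**The case against.** The strongest reply is that little is lost in practice. Four parts of it deserve an answer.

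- A reader might infer that hypotension can never be flagged anywhere in the report. The documents do not support that. As Step 3 shows, reported hypotension and CRS have three routes into the summaries. This part of the reply stands, and the point is limited to the measured-value limits.
- A reader might also infer that reported CRS events could not be checked against measured pressure. That is not so either. A missing flag deletes no readings. Protocol 9.4.2 calls for summaries by nominal visit and a worst-case analysis across on-treatment time points. The SAP's default continuous summary includes the minimum (SAP 4.1.1), and further data can be viewed electronically (SAP section 1). With about 22 participants planned in Part 1, pressures can be set beside each event.
- A low limit would not verify CRS grade. Protocol Table 11 gives no pressure threshold and separates Grades 2 to 4 by vasopressor need or oxygen support. This is correct; the case for a low limit is completeness of the safety summary, not re-grading of CRS.
- The amended SAP supports only a synoptic report, so the table may never be produced. That makes the effect conditional but leaves the gap in place: the protocol commitment is neither carried out with usable criteria nor recorded as dropped.

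The reference to CTCAE in SAP 6.2.1 does not fill the gap, because the only blood-pressure limits the SAP prints are the upward bands.

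**Conclusion.** The point holds in a limited form and is worth correcting. The limits in SAP 6.2.1.2 are one-sided for blood pressure, and any clinical-importance summary built on them would show no low reading at any dose. This follows directly from the printed limits. The practical effect rests on one assumption, that such a summary is still produced; the protocol and SAP leave it in force without specifying it.

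It would go too far to infer an effect on dosing or on bedside CRS grading. Escalation relies on dose-limiting toxicities and review of all available safety data (Protocol 4.1 and 4.1.2), and CRS is graded from Protocol Table 11. No misclassified result has been shown.

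**What to change.** In SAP 6.2.1.2, add a pre-specified low category for systolic and for diastolic pressure, taken from the sponsor's own standards, and report it by dose level beside the high categories. The documents give no low limit and none is proposed here. Because recruitment to Part 1 has ended, label the category as added after study termination.

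If no vital-sign summary will be produced, record that in SAP 4.8 as a change from Protocol 9.4.2.4, and state that low pressure is assessed through adverse event reporting and the recorded values.

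A summary of the largest decrease from pre-dose would be informative but is optional, since the protocol does not call for it.

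The cost is two table rows and a small programming change on data already scheduled for collection, provided the sponsor has standard low limits to draw on. The alternative costs one sentence in SAP 4.8.

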### 6.2.2. Study Period

Assessments and events will be classified according to the time of occurrence relative to the study intervention period.

**Pre-Intervention** is defined as time prior to the first dose of study intervention.

**On-Intervention** is defined as time from first dose to last date plus 30 days. If time of assessment or study intervention is not collected, the following assessment on the first dose date will be assumed to be taken prior to the first dose and therefore considered preintervention: ECOG, ECG, Lab, and vital signs, and first dose date is considered on-intervention for AE and concomitant medication.

**Post-Intervention** is defined as any time post on-intervention window, i.e. > last dose date + 30 days.

Anti-cancer therapy will be classified as either prior to screening or following study treatment as per GSK Display Standards.

### 6.2.2.1. Treatment Emergent Flag for Adverse Events

Flag	Definition
Treatment Emergent	For AEs:  • Study Treatment Start Date ≤ AE Start Date ≤ Treatment Discontinuation Visit or Study Treatment Stop Date + 30 Days if TDV is missing  • AE Start Date is missing
	
 
For SAEs/AESIs:
 
Study Treatment Start Date ≤ AE Start Date or pre-existing (prior to exposure) AE Worsening Date ≤ Study Treatment Stop Date + 90 days or Start of Anti-Cancer Therapy, whichever occurs first
 
AE Start Date is missing
 

	Missing AE Start Date will be imputed following rules in Appendix 2 for determining Treatment Emergent AEs.

### NOTES:

If the study treatment stop date is missing, then the AE will be considered to be On-Treatment.

### 6.2.3. Study Day and Reference Dates

The safety reference date is the study intervention start date and will be used to calculate study day for safety measures.

The efficacy reference date is the study intervention start date and will be used to calculate study day for efficacy measures and baseline characteristics, as well as efficacy durations.

The study day is calculated as below:

- Assessment Date = Missing → Study Day = Missing
- Assessment Date < Reference Date → Study Day = Assessment Date Ref Date
- Assessment Data  $\geq$  Reference Date  $\rightarrow$  Study Day = Assessment Date Ref Date + 1

#### 6.2.4. Assessment Window

For data summaries by visit, the nominal visit description will be used.

For PK data, the data from unscheduled visits will be slotted as follows:

Elapsed time from dose to start of PK sample collection(ARELTM) in hours is calculated as = (start datetime of PK sample collection – reference dose datetime) /3600.

Elapsed time from dose to start of PK sample collection(ARELTM) in minutes is calculated as = (start datetime of PK sample collection – reference dose datetime) /60.

Slotting algorithm if elapsed time(ARELTM) is in minutes:

- 0 < ARELTM <= 1, ARELTM = 1 min
- 1< ARELTM <=5, ARELTM = 5 min
- 5 < ARELTM <=15, ARELTM = 15 min
- 25 <= ARELTM <=35, ARELTM = 30 min
- 40<=ARELTM<=50, ARELTM = 40 min

Slotting algorithm if elapsed time (ARELTM) is in hours:

- $0.75 \le ARELTM \le 1.25$ , ARELTM = 1 hr
- 1.50 <= ARELTM <=2.50, ARELTM = 2 hrs
- $3 \le ARELTM \le 5$ , ARELTM = 4 hrs
- $7 \le ARELTM \le 9$ , ARELTM = 8 hrs
- 22 <= ARELTM < =26, ARELTM = 24 hrs

### 6.2.5. Multiple measurements at One Analysis Time Point

Mean of the measurements will be calculated and used in any derivation of summary statistics but if listed, all data will be presented (including the mean). For PK data, if there are multiple records observed at the same date and time for a subject, those data will be excluded from the WNL file and will not be used for the derivation of PK parameters.

Participants having both High and Low values for Normal Ranges at any post-baseline visit for safety parameters will be counted in both the High and Low categories of "Any visit post-baseline" row of related summary tables. This will also be applicable to relevant Potential Clinical Importance summary tables.

# 6.2.6. Handling of Partial Dates

Element	Reporting Detail	
General	
 
Partial dates will be displayed as captured in participant listing displays.
 
However, where necessary, display macros may impute dates as temporary variables for sorting data in listings only. In addition, partial dates may be imputed for 'slotting' data to study phases or for specific analysis purposes as outlined below.
 
Imputed partial dates will not be used to derive study day, time to onset or duration (e.g., time to onset or duration of adverse events), or elapsed time variables (e.g., time since diagnosis). In addition, imputed dates are not used for deriving the last contact date in overall survival analysis dataset.
 
	
Adverse Events	
 
Partial dates for AE recorded in the CRF will be imputed using the following conventions:
 
Missing start day
 
If study intervention start date is missing (i.e., participant did not start study intervention), then set start date = 1st of month.
 
Else if study intervention start date is not missing:
 
If only a single dose level was given in the same month, then AE start date = 1st of the month or treatment start date (whichever is later).
 
If more than one dose level was given in the same month as the AE start date, then,
 
If AE end date contains a full date and AE end date is earlier than study intervention start date of the highest dose given that month, then set AE start date= 1st of month.
 
If AE end date contains a full date and AE end date is later than the study intervention start date of the highest dose given that month, then AE start date = study intervention start date of highest dose given that month.
 
If AE end date is missing, then set AE start date as the study intervention start date of the highest dose given that month.
 
Else set start date = 1st of month.
 
	
	Missing start day and month  If study intervention start date is missing (i.e., participant did not start study intervention), then set AE start date = January 1.  Else if study intervention start date is not missing:  If year of AE start date = year of study intervention start date, then	

	B 41 - 5 4 11	209809
Element	Reporting Detail	
		
 
If AE stop date contains a full date and AE stop date is earlier than study intervention start date, then set AE start date = January 1.
 

		
 
If AE stop date contains a full date and AE stop date is later than study intervention start date, then set start date = study intervention start date of most recent dose level given prior to the AE stop date.
 

		Else set AE start date = January 1.
	Missing end day	A '28/29/30/31' will be used for the day (dependent on the month and year).
	Missing end day and month	No Imputation
	Completely missing start/end date	No imputation. Consequently, time to onset and duration of such events will be missing.
Concomitant Medications/	Partial dates for using the follow	any concomitant medications recorded in the CRF will be imputed ing convention:
Medical History	Missing start day	If study intervention start date is missing (i.e., participant did not start study intervention), then set start date = 1st of month.
		Else if study intervention start date is not missing:
		If month and year of start date = month and year of study intervention start date, then
		
 
If stop date contains a full date and stop date is earlier than study intervention start date, then set start date= 1st of month.
 

		Else set start date = study intervention start date.
		Else set start date = 1st of month.
	Missing start day and month	If study intervention start date is missing (i.e., participant did not start study intervention), then set start date = January 1.
		Else if study intervention start date is not missing:
		If year of start date = year of study intervention start date, then
		
 
If stop date contains a full date and stop date is earlier than study intervention start date, then set start date = January 1.
 

		Else set start date = study. intervention start

Element	Reporting Detail	209809
Element	Reporting Detail	date.
		oate.
		Else set start date = January 1.
	Missing end day	A '28/29/30/31' will be used for the day (dependent on the
		month and year).
	Missing end day and month	A '31' will be used for the day and 'Dec' will be used for the month.
	Completely missing start/end date	No imputation
Prior Anti- cancer Therapy/Radi othe	an analysis (e.g., to conficacy analyses), following of anti-cancer therapy	• •
rapy/Surgical Procedures/S		ate is completely missing or both day and month are missing, no ill be applied
tem Cell Transplant	
 
If day is miss
 
	sing for start date, first of the month will be used
Tranoplant	
 
If day is miss
 
	sing for stop date,
		rst dosing date is the first of the month, minimum of dates (impute last of the partial date month to partial date, first dosing date) will be d
		m of dates (impute last day of the partial date month to partial date, late - 1) will be used
New Anti- cancer Therapy/ Radiotherapy/ Surgical Procedures/C ross over for	transplant, and surgic event and censoring r response (i.e. start da month and year are a impute the date when	up anti-cancer therapy, radiotherapy (where applicable), stem cell al procedures (where applicable) will be imputed in order to define rules for progression-free survival, response rate, or duration of the for new anti-cancer therapy). Dates will only be imputed when a vailable, but the day is missing. The following rules will be used to partial start dates are present on anti-cancer therapy, radiotherapy, and/or surgical procedures dataset[s]:
Efficacy	
 
Completely missi
 
	ng start dates will remain missing, with no imputation applied;
Evaluation (e.g.,	
 
Partial start dates
 
	s will be imputed using the following convention:
response	

If both n

	nonth and day are missing, no imputation will be applied;
rate, time to	

If only d

	ay is missing:
event)	•	If the month of partial date is the same as the month of last dosing date, minimum of dates (last dosing date + 1, impute last day of the partial date month to partial date) will be used for the day;
	•	If the month of partial date is the same as the month of last disease assessment and the last disease assessment is PD for MDS (Recurrences for AML), minimum of dates (last date of disease assessment + 1, impute last day of the partial date month to partial date) will be used for the date;
	•	If both conditions above are met, the later date will be used for the day;
	•	Otherwise, a '01' will be used for the day;

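### SAP 6.2.6: two gaps in the partial-date rules can place an on-treatment AE before first dose, or leave it with no rule

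*SAP*

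**What the plan says.** **Flag (SAP 6.2.2.1).** An ordinary AE is emergent if "Study Treatment Start Date ≤ AE Start Date ≤ Treatment Discontinuation Visit", or up to 30 days after treatment stop if that visit is missing. It is also emergent if "AE Start Date is missing". The section adds: "Missing AE Start Date will be imputed following rules in Appendix 2 for determining Treatment Emergent AEs". For a completely missing date, SAP 6.2.6 says "No imputation. Consequently, time to onset and duration of such events will be missing", so the flag rule alone decides and the event counts as emergent.

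**Start day missing (SAP 6.2.6).** With one dose level in the month: "then AE start date = 1st of the month or treatment start date (whichever is later"). With more than one level, if there is a full end date and "AE end date is earlier than study intervention start date of the highest dose given that month", the start is the 1st of the month, and treatment start is not mentioned. If the end date is later than the start of the highest dose, or is missing, the AE starts when the highest dose started.

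**Day and month missing (SAP 6.2.6).** Under "If year of AE start date = year of study intervention start date, then" there are two cases. A full stop date before first dose gives January 1. A full stop date after first dose gives the start of the most recent dose level. The next line is "Else set AE start date = January 1". The concomitant-medication block has the same shape, but an inner default to first dose comes before its January 1 line.

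**Use (SAP 4.2.2).** AE summary tables are built on TEAEs. All AEs are listed.

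**The concern.** The AE summaries serve the primary objective of Part 1, and an imputed date before first dose takes an event out of them. Two neighbouring branches treat the same uncertainty differently: one is floored at treatment start and the other is not. The AE block also lacks the inner default that the medication block has. As a result, an event whose month is known can be excluded when the same event with no date at all would be included.

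This sits badly with the rest of the plan. SAP 4.2.2 takes a worst-case approach to missing relatedness. SAP 6.2.2 treats the day of first dose as on-intervention for AEs. Protocol 8.3.1 sends occurrences that begin between consent and first dose to medical history, so a recorded AE should normally have begun on treatment.

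**Working it through.** The plan states no figure to reproduce. The check applies the written rules to dates.

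**Inputs.** Cycles last 28 days, and the dose may double at Cycle 2 (Protocol 1.1 and 4.1). The imputation rules are in SAP 6.2.6 and the flag in SAP 6.2.2.1. Assumptions: a non-leap year (2023), no delay between cycles, escalation at Cycle 2.

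**Several dose levels in the month of first dose.** Let first dose fall on day *d* of a month with *L* days.

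- Cycle 2 starts in the same month if *d* + 28 ≤ *L*.
- The 1st of the month precedes first dose if *d* ≥ 2.
- *L* = 31: *d* = 2 or 3. *L* = 30: *d* = 2. *L* = 28: none.
- Count: 7 × 2 + 4 × 1 = 18 of 365 first-dose dates, or 4.9%.

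In later months the 1st already follows first dose, so the missing floor does no harm.

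Example: first dose 2 March; Cycle 2 at a higher dose on 2 + 28 = 30 March; an AE that began on treatment in March, start day unknown.

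| What is recorded | Imputed start | Emergent? |
|---|---|---|
| Ended 20 March, escalated 30 March | 1 March | No (1 March < 2 March) |
| Ended 20 March, no escalation in March | later of 1 and 2 March = 2 March | Yes |
| No end date, escalated 30 March | 30 March | Yes |
| No start date at all | none | Yes |

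Only the first row is excluded, and this result does not depend on how any *Else* is read.

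**Year-only start in the year of first dose.** An ongoing AE, a partial stop date, or a stop date equal to first dose meets neither stop-date case. The outcome depends on the final *Else*:

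- *Catch-all.* The start becomes January 1, which precedes first dose for 364 of 365 first-dose dates (all but January 1 itself). With first dose on 12 June 2023, an ongoing AE dated 2023 becomes 1 January 2023 and is not emergent.
- *Attached to the year condition only.* The line then covers AEs from other years. A later-year AE goes to January 1 of that year, after first dose, which is harmless. An earlier-year AE correctly stays before treatment. The same-year ongoing AE has no rule for 365 of 365 dates.

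**After the fix below.** The first row becomes the later of 1 and 2 March = 2 March, emergent. The 12 June example becomes 12 June, emergent. Pre-dose imputations on both routes fall to 0, except where the stop date shows that the AE ended before first dose.

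**The case against.** **The January 1 line may not do what it seems to.** A reader might infer that every year-only AE without a stop date is dated January 1 and lost. The documents do not establish this. The table's indentation does not survive in the text available, and in the medication block the January 1 line pairs with the year condition. Read that way, a same-year ongoing AE is left unimputed, and if it is then treated as missing it counts as emergent. This stands: what can be asserted is an unclear or absent rule.

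**The clear case is narrow and mild.** It needs one of 18 first-dose dates, a same-month escalation, an unknown start day and a full end date before the higher dose. Participants are inpatients from Day -1 to Day 13 of each cycle and are phoned after discharge (Protocol 1.3.1), so an unknown onset day should be uncommon. Escalation also requires no Grade ≥3 AE and no DLT (Protocol 4.1.2 and 6.4.1.1), so an AE that ended before a permitted escalation should be Grade 1 or 2. Both points stand, and they limit the importance.

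**The rules do not lean one way overall.** A reader might infer a general bias against TEAEs. The other branches do not support that: one dose level is floored at treatment start, a missing end date with several levels goes to the highest dose, and a later full stop date goes to a dose start. Nor is every exclusion certain to be wrong, because Protocol 8.3.1 has SAEs related to study participation recorded from consent.

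**A blanket floor would cause new errors.** An ongoing AE dated 2022 with first dose in June 2023 would be moved to June 2023. An AE dated 2023 that stopped in February 2023 would start after its imputed end of 28 February. This stands, and it restricts the fix.

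**Conclusion.** The point holds in limited form, as a minor correction. The branch for several dose levels lacks the floor used in the single-level branch and can remove an on-treatment AE from the TEAE summaries. The year-only branch lacks an inner default, so its result is either January 1 or undefined.

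The size is small. The first gap can arise for 18 of 365 first-dose dates, assuming exact 28-day cycles and escalation at Cycle 2, and then only for an AE with this pattern of dates. The documents do not say how many AEs have partial dates, so the number affected is unknown. One event could still matter to the summary of common non-serious TEAEs, which uses a strict 10% cut-off. Taking the planned 22 participants of Part 1 as denominator (the actual number is not given), a term falling from 3/22 = 13.6% to 2/22 = 9.1% would leave that table.

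A reader might infer that the safety conclusions or DLT counts are at risk. The documents do not support that. All AEs are listed, imputed dates are not used for study day, onset or duration (SAP 6.2.6), and the DLT summary rests on the DLT-evaluable set and is not said to depend on the flag.

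**What to change.** 1. **Several dose levels in the month.** Where the AE's month and year are those of first dose, set the start to the 1st or to first dose, whichever comes later, unless the stop date precedes first dose.
2. **Year-only start.** Where the AE's year is that of first dose, add an inner default to first dose, as in the medication block, unless a full stop date, or a partial one imputed under SAP 6.2.6, precedes first dose. State that the final *Else* applies only when the years differ.
3. **Leave alone** any AE recorded in a month or year before that of first dose.

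The cost is one or two lines of code and possibly slightly more TEAEs. SAP 4.8 says Part 1 recruitment has finished, so the AE data can be searched for events meeting either condition. If there are none, a note to that effect is enough.
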